11.11.5.5. Safety Tables (Part C)

Safety: Tables					
No.	Population	IDSL / Example Shell	Title	Programming Notes	Deliverable [Priority]
Adverse Events (AEs)					
3.53.	ITT (Part C)	SHELL	Overview of Adverse Events (Part C)		SAC
3.54.	ITT (Part C)	AE1	Summary of On-Treatment Adverse Events by System Organ Class and Preferred Term (Part C)	ICH E3	SAC
3.55.	ITT (Part C)	AE5	Summary of On-Treatment Adverse Events by Maximum Intensity by System Organ Class and Preferred Term (Part C)	ICH E3 Add a Total column across all severities	SAC
3.56.	ITT (Part C)	SHELL	Summary of Exposure Adjusted On-Treatment Adverse Events by System Organ Class and Preferred Term (Part C)		SAC
3.57.	ITT (Part C)	AE3	Summary of Common ( $\geq 3\%$ ) On-treatment Adverse Events by Overall Frequency (Part C)	ICH E3 $\geq 3\%$ (prior to rounding to nearest percent)	SAC
3.58.	ITT (Part C)	SHELL	Summary of Exposure Adjusted On-Treatment Common ( $\geq 3\%$ ) Adverse Events by System Organ Class and Preferred Term (Part C)	$\geq 3\%$ (prior to rounding to nearest percent)	SAC
3.59.	ITT (Part C)	AE1	Summary of On-Treatment Drug-Related Adverse Events by System Organ Class and Preferred Term (Part C)	ICH E3	SAC
3.60.	ITT (Part C)	AE5	Summary of On-Treatment Drug-Related Adverse Events by System Organ Class and Preferred Term and Maximum Intensity (Part C)	Add a Total column across all severities	SAC
3.61.	ITT (Part C)	SHELL	Summary of Exposure Adjusted On-Treatment Drug-Related Adverse Events by System Organ Class and Preferred Term (Part C)		SAC
3.62.	ITT (Part C)	SHELL	Summary of On-Treatment Adverse Events by Age Group (12-17, 18-64, $\geq 65$ years) (Part C)		SAC
3.63.	ITT (Part C)	SHELL	Summary of On-Treatment Adverse Events by Highest Anti Drug Antibody Result At Any Time On-Treatment (Part C)		SAC

Safety: Tables					
No.	Population	IDSL / Example Shell	Title	Programming Notes	Deliverable [Priority]
3.64.	ITT (Part C)	AE15	Summary of Common ( $\geq 3\%$ ) Non-serious On-Treatment Adverse Events by System Organ Class and Preferred Term (Number of Subjects and Occurrences) (Part C)	FDAAA, EudraCT $\geq 3\%$ (prior to rounding to nearest percent)	SAC
3.65.	ITT (Part C)	AE1	Summary of On-Treatment Drug-Related Non-Serious Adverse Events by System Organ Class and Preferred Term (Part C)	Table required for plain language summary	SAC
Serious and Other Significant Adverse Events					
3.66.	ITT (Part C)	AE1	Summary of On-Treatment Serious Adverse Events by System Organ Class and Preferred Term (Part C)		SAC
3.67.	ITT (Part C)	SHELL	Summary of Exposure Adjusted On-Treatment Serious Adverse Events by System Organ Class and Preferred Term (Part C)		SAC
3.68.	ITT (Part C)	SHELL	Summary of On-Treatment Serious Adverse Events by Age Group (12-17, 18-64, $\geq 65$ years) (Part C)		SAC
3.69.	ITT (Part C)	AE1	Summary of On-Treatment Fatal Serious Adverse Events (Part C)		SAC
3.70.	ITT (Part C)	SHELL	Summary of On-Treatment Fatal Serious Adverse Events by Age Group (12-17, 18-64, $\geq 65$ years) (Part C)		SAC
3.71.	ITT (Part C)	AE1	Summary of On-Treatment Non-Fatal Serious Adverse Events by System Organ Class and Preferred Term (Part C)		SAC
3.72.	ITT (Part C)	AE1	Summary of On-Treatment Drug-Related Serious Adverse Events by System Organ Class and Preferred Term (Part C)	Table required for plain language summary	SAC
3.73.	ITT (Part C)	AE1	Summary of On-Treatment Adverse Events Leading to Permanent Discontinuation of Study Treatment or Withdrawal from Study by System Organ Class and Preferred Term (Part C)	IDSL	SAC
3.74.	ITT (Part C)	AE16	Summary of On-Treatment Serious Adverse Events by System Organ Class and Preferred Term (Number of Subjects and Occurrences) (Part C)	FDAAA, EudraCT	SAC

Safety: Tables					
No.	Population	IDSL / Example Shell	Title	Programming Notes	Deliverable [Priority]
Adverse Events of Special Interest					
3.75.	ITT (Part C)	SHELL	Summary of On-treatment Serious Adverse Events and Adverse Events of Special Interest (Incidence, Relative Risk and Risk Difference) (Part C)		SAC
3.76.	ITT (Part C)	AE1	Summary of On-Treatment Systemic Reactions Meeting Anaphylaxis Criteria (Part C)	Present by Anaphylactic Criterion 1, 2 and 3 rather than SOC as shown in AE1 Insert footnote: "Events displayed are a subset of reactions defined by the Investigator as being systemic"	SAC
3.77.	ITT (Part C)	SHELL	Summary Profile of On-Treatment Systemic Reactions Meeting Anaphylaxis Criteria (Part C)	Insert footnote: "Events displayed are a subset of reactions defined by the Investigator as being systemic"	SAC
3.78.	ITT (Part C)	AE1	Summary of On-Treatment Adverse Events Defined by the Investigator as Being Systemic (non-allergic or allergic/hypersensitivity) Reactions (Part C)		SAC
3.79.	ITT (Part C)	SHELL	Summary Profile of On-Treatment Systemic (non-allergic or allergic/hypersensitivity) Reactions (Part C)		SAC
3.80.	ITT (Part C)	SHELL	Summary Profile of On-Treatment Systemic Allergic Reactions (Part C)		SAC
3.81.	ITT (Part C)	SHELL	Summary Profile of On-Treatment Systemic Non-Allergic Reactions (Part C)		SAC
3.82.	ITT (Part C)	AE1	Summary of On-Treatment Adverse Events Defined by the Investigator as being Local Injection Site Reactions (Part C)		SAC
3.83.	ITT (Part C)	SHELL	Summary Profile of On-Treatment Local Injection Site Reactions (Part C)		SAC
3.84.	ITT (Part C)	AE1	Summary of On-Treatment Opportunistic Infections (Part C)		SAC
3.85.	ITT (Part C)	SHELL	Summary Profile of On-Treatment Opportunistic Infections (Part C)		SAC
3.86.	ITT (Part C)	AE1	Summary of On-Treatment Malignancies (Part C)		SAC

Safety: Tables					
No.	Population	IDSL / Example Shell	Title	Programming Notes	Deliverable [Priority]
3.87.	ITT (Part C)	SHELL	Summary Profile of On-Treatment Malignancies (Part C)		SAC
3.88.	ITT (Part C)	AE1	Summary of On-Treatment Serious Cardiac, Vascular and Thromboembolic Adverse Events (Part C)		SAC
3.89.	ITT (Part C)	SHELL	Summary Profile of On-Treatment Serious Cardiac, Vascular and Thromboembolic Adverse Events (Part C)		SAC
3.90.	ITT (Part C)	AE1	Summary of On-Treatment Serious Ischemic Adverse Events (Part C)		SAC
3.91.	ITT (Part C)	SHELL	Summary Profile of On-Treatment Serious Ischemic Adverse Events (Part C)		SAC
Cardiovascular Events and Deaths (All Causes)					
3.92.	ITT (Part C)	SHELL	Summary of Cardiovascular Events and Deaths (All Causes) Reported by the Investigator (On-Treatment, Part C)		SAC
Laboratory: Chemistry					
3.93.	ITT (Part C)	LB1	Summary of Chemistry Changes from Baseline (On-Treatment, Part C)	ICH E3 Includes Baseline values.	SAC
3.94.	ITT (Part C)	LB3	Summary of Chemistry Results (Changes from Baseline Relative to the Normal Range) (On-Treatment, Part C)	ICH E3	SAC
3.95.	ITT (Part C)	LB3	Summary of Chemistry Results (Changes from Baseline Relative to the Reference Range [Potential Clinical Importance]) (On-Treatment, Part C)	ICH E3	SAC
Laboratory: Haematology					
3.96.	ITT (Part C)	LB1	Summary of Haematology Changes from Baseline (On-Treatment, Part C)	ICH E3 Includes baseline values.	SAC
3.97.	ITT (Part C)	LB3	Summary of Haematology Results (Changes from Baseline Relative to the Normal Range) (On-Treatment, Part C)	ICH E3	SAC
3.98.	ITT (Part C)	LB3	Summary of Haematology Results (Changes from Baseline Relative to the Reference Range [Potential Clinical Importance]) (On-Treatment, Part C)	ICH E3	SAC

Safety: Tables					
No.	Population	IDSL / Example Shell	Title	Programming Notes	Deliverable [Priority]
Laboratory: Hepatobiliary (Liver)					
3.99.	ITT (Part C)	LIVER10	Summary of Hepatobiliary Laboratory Abnormalities (On-Treatment, Part C)	IDSL	SAC
ECG					
3.100.	ITT (Part C)	EG1	Summary of ECG Findings (On-Treatment, Part C)	IDSL	SAC
3.101.	ITT (Part C)	EG2	Summary of Change from Baseline in ECG Values by Visit (On-Treatment, Part C)	IDSL Includes Baseline values.	SAC
3.102.	ITT (Part C)	SHELL	Summary of Actual and Change From Baseline QTc(F) Values by Category (msec) (On-Treatment, Part C)		SAC
3.103.	ITT (Part C)	SHELL	Summary of Actual and Change From Baseline QTc(B) Values by Category (msec) (On-Treatment, Part C)		SAC
Vital Signs					
3.104.	ITT (Part C)	VS1	Summary of Change from Baseline in Vital Signs (On-Treatment, Part C)	ICH E3 Includes Baseline values.	SAC
Immunogenicity					
3.105.	ITT (Part C)	SHELL	Summary of ADA Assay Results (On-Treatment, Part C)		SAC
3.106.	ITT (Part C)	SHELL	Summary of Treatment Emergent ADA Assay Results (On-Treatment, Part C)		SAC
3.107.	ITT (Part C)	SHELL	Summary of NAb Assay Results (On-Treatment, Part C)		SAC

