10. STATISTICAL CONSIDERATIONS AND DATA ANALYSES

10.1. Hypotheses

The study is designed to test the superiority of continued mepolizumab 100 mg SC treatment vs. mepolizumab discontinuation (placebo). Significance tests will be performed at the two-sided 5% alpha level (one-sided 2.5%).

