10.2.1. Sample Size Assumptions

With a sample size of 300 randomised subjects (150 per arm), it is estimated that statistical significance will be declared if the proportion of subjects with a clinically significant exacerbation following withdrawal of mepolizumab is 52.5% compared to 40% for those continuing to receive mepolizumab (hazard ratio = 0.686).

If the true hazard ratio is 0.55 (corresponding to a proportion with an exacerbation following discontinuation of mepolizumab of 60.5%), then the study has a probability of 90% of observing a hazard ratio of < 0.686 and therefore the study has 90% power for declaring statistical significance on this endpoint.

The estimated event rate for subjects randomized to mepolizumab is based on interim data from study MEA115666 which suggests 40% of subjects will experience an exacerbation within one year of randomization. In study MEA115588, the observed hazard ratio for the combined treatment arms of mepolizumab 100mg SC and 75mg SC vs placebo was 0.5. A lower event rate among those discontinuing mepolizumab is expected in this study than was observed for placebo in MEA115588 because of the continuing effects of previous treatment with mepolizumab. The sample size calculations assume 20% of subjects will withdraw prior to the end of the double-blind treatment phase before experiencing an exacerbation.

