### 8.1. Adverse Events Analyses

Adverse events analyses including the analysis of adverse events (AEs), Serious (SAEs) and other significant AEs will be based on GSK Core Data Standards.

AEs occurring during the on-treatment phase will be summarised separately for each period (Parts A/B, Part C and Part D). Adverse events will be coded using the latest version of the Medical Dictionary for Regulatory Activities (MedDRA).

The number and percentage of subjects experiencing at least one AE will be summarised. Exposure adjusted rates of AEs during Part C will also be presented to account for the length of subject exposure within the double-blind treatment period. For the definition of exposure adjusted AEs, see Section 11.6.4.

The details of the planned displays are provided in [Appendix 11](#): List of Data Displays.

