11.11.5.6. Safety Figures (Part C)

Safety: Figures					
No.	Population	IDSL / Example Shell	Title	Programming Notes	Deliverable [Priority]
Adverse Events					
3.1.	ITT (Part C)	AE10	Plot of Common ( $\geq 3\%$ ) On-treatment Adverse Events and Relative Risk (Part C)	IDSL $\geq 3\%$ (prior to rounding to nearest percent)	SAC
3.2.	ITT (Part C)	SHELL	Figure of On-treatment Serious Adverse Events and Adverse Events of Special Interest (Relative Risk, 100mg SC vs Placebo) (Part C)		SAC

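### The Part C between-arm AE contrasts appear to use crude incidence although switching to Part D is expected to shorten placebo follow-up; rate-based contrasts should stand beside them

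*SAP*

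**What the plan says.** The between-arm AE contrasts listed for Part C in SAP Appendix 11 are:

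- Table 3.75: "Summary of On-treatment Serious Adverse Events and Adverse Events of Special Interest (Incidence, Relative Risk and Risk Difference) (Part C".
- Figure 3.1, for common AEs, whose title ends "On-treatment Adverse Events and Relative Risk (Part C".
- Figure 3.2: "Figure of On-treatment Serious Adverse Events and Adverse Events of Special Interest (Relative Risk, 100mg SC vs Placebo) (Part C".

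None is labelled exposure adjusted. Four other Part C tables are: 3.56 (all AEs), 3.58 (common AEs), 3.61 (drug-related AEs) and 3.67 (serious AEs). They follow from SAP 8.1: "Exposure adjusted rates of AEs during Part C will also be presented to account for the length of subject exposure". SAP 11.6.4 defines that rate as the number of events per 1000 subject-years of total exposure. It defines no ratio or difference of rates. SAP 8.1.1 summarises each AESI type by count and percentage of subjects, and Tables 3.76-3.91 contain no exposure-adjusted AESI display.

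Under SAP 11.4.4, on-treatment AE time for a switcher stops at the first Part D dose. Protocol 5.1 opens Part D after a clinically significant exacerbation, and a switch decided between visits takes effect at the next 4-weekly visit. Protocol 5.3 anticipates about 120 subjects who exacerbate and meet the switch criteria.

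**The concern.** The protocol's secondary objective is the safety and tolerability of continuing mepolizumab compared with placebo. If the plan's efficacy assumption is right, placebo subjects leave Part C sooner and have less time in which an AE can be counted. A ratio of crude percentages then lies above 1 for an AE that the drug does not affect. The SAP recognises unequal exposure when it describes each arm, but does not carry the adjustment into the displays that compare the arms. A reader who takes the safety comparison from Table 3.75 or the two figures could mistake a difference in follow-up for a drug effect.

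**Working it through.** **Inputs.** Protocol 10.2.1: "With a sample size of 300 randomised subjects (150 per arm"; for mepolizumab, interim data "which suggests 40% of subjects will experience an exacerbation within one year of randomization"; for placebo, "If the true hazard ratio is 0.55 (corresponding to a proportion with an exacerbation following discontinuation of mepolizumab of 60.5". The same section assumes that 20% withdraw before an exacerbation. Protocol 10.1: "Significance tests will be performed at the two-sided 5% alpha level (one-sided 2.5". The documents give no switch uptake and no exposure ratio. Uptake is therefore varied, and AE and exacerbation hazards are assumed constant and independent of each other.

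**Reproducing the plan's own figures.**
- Placebo proportion: 1 - 0.6^(1/0.55) = 60.5%.
- Expected events: 150 × (0.40 + 0.605) × 0.80 = 120.6. This matches the protocol's roughly 120 switch-eligible subjects, so near-full uptake is the document-based central case.
- Schoenfeld power: √(120.6/4) × |ln 0.55| - 1.96 = 5.49 × 0.598 - 1.96 = 1.32, giving 90.7% against the stated 90%.

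**Exposure if every exacerbator switches at onset, without withdrawal.** The yearly hazards are -ln 0.60 = 0.511 and -ln 0.395 = 0.929. Mean time in Part C is (1 - e^(-h))/h:
- mepolizumab: 0.40/0.511 = 0.783 year (40.7 weeks)
- placebo: 0.605/0.929 = 0.651 year (33.9 weeks)
- ratio: 1.20

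**Adding withdrawal.** A withdrawal hazard of 0.32 per year reproduces the 20%: 21.7% and 18.3% withdraw first in the two arms. The total hazards become 0.831 and 1.249, the means 35.3 and 29.7 weeks, and the ratio 1.19.

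**Adding the visit lag (simulated).** With withdrawal and a switch at the next 4-weekly visit, the means are 36.0 and 30.8 weeks, ratio 1.17. A further 4-week delay gives 37.3 and 32.7 weeks, ratio 1.14.

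**Partial uptake.** If each exacerbator switches with probability s, then at onset and without withdrawal the mean is (1 - s) + s × (full-uptake mean). For s = 0.5 this gives 0.892 against 0.826 year, ratio 1.08. The ranges below also cover withdrawal and visit lag.

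| Uptake among exacerbators (HR 0.55) | Exposure ratio, and crude RR for a rare AE with equal rates |
|---|---|
| nearly all | 1.14-1.20 |
| 75-80% | 1.10-1.15 |
| 50% | 1.06-1.08 |

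With full uptake, withdrawal and the next-visit lag, the ratio is about 1.09 at HR 0.686 and 1.00 at HR 1. If uptake differs by arm (70% mepolizumab against 90% placebo, or 50% against 80%), it is about 1.20 at HR 0.55.

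**From exposure to crude incidence.** For an AE with yearly rate a, crude incidence is a/(a + h) × (1 - e^(-(a+h))), where h is the hazard of leaving Part C. For small a this is close to a times the mean exposure, so the RR is close to the exposure ratio. Take an annual risk of 5% (a = 0.0513), full uptake at onset and no withdrawal: 3.92% against 3.27%, RR 1.20, difference 0.65 points. With withdrawal and the next-visit lag the difference is 0.5 points at 5% annual risk and 0.1 points at 1%, with RR 1.17.

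**The case against.** The strongest reply is that SAP 8.1 already deals with unequal exposure. Tables 3.56, 3.58, 3.61 and 3.67 give rates by arm, a reader can divide one by the other, and SAP 8 describes safety data as summarised descriptively, so no decision rests on Table 3.75. This stands in part: for AEs and SAEs a careful reader could detect the artefact. But those rates count events, whereas the relative risk counts subjects, so dividing them does not correct the RR. No interval is planned for such a ratio either.

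Three stronger readings are tempting, and the documents do not support them:

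- A reader might infer that AESIs have no exposure-adjusted data at all. Their component terms fall within Table 3.56 and, if serious, Table 3.67. What is missing is a rate for each AESI group.
- A reader might infer a fixed bias against mepolizumab built into every row. Switching is optional and at the investigator's discretion (Protocol Table 3), and the size depends on uptake and the true hazard ratio. Protocol 8.3.2.1 also lets exacerbations that meet the SAE definition be recorded as AEs. These are expected more often on placebo, so serious-event rows may also move the other way.
- A reader might take crude incidence as established. It is inferred from the titles and from the count-and-percentage wording, because SAP Appendix 12 leaves the shells available on request.

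The distortion is also small beside sampling error. At 5% incidence per arm with 150 subjects each, the standard error of ln RR is √(2 × 0.95/7.5) = 0.50, so the 95% interval spans a factor of about 2.7 either way.

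**Conclusion.** The point holds as an inexpensive improvement to how safety is compared. At the plan's own assumptions the three contrasts do not centre on 1 for an AE that the drug does not affect: the expected RR is about 1.14-1.20 with near-full switching and falls to 1.06-1.08 at 50% uptake. The absolute effect at 1-5% annual risk is about 0.1-0.5 points, and 0.65 in the most extreme case computed. This rests on a hazard ratio near 0.55, constant AE hazards independent of exacerbation, and the reading of the displays as crude. The argument is cleanest for non-asthma AEs and AESIs. It does not show that the plan overlooks exposure, nor that the planned crude displays should be dropped.

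**What to change.** Keep the crude relative risk and risk difference. In Table 3.75 and Figures 3.1 and 3.2, set beside them an exposure-adjusted incidence rate ratio and rate difference with 95% CIs. The numerator is subjects with a first event; the denominator is time at risk to that event or to the end of the on-treatment period. Include one row per AESI group. Add this definition to SAP 11.6.4, where the existing formula counts all events over total exposure, and state that the between-arm safety conclusion rests on the rate-based measures.

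The cost is one new definition, programming for one table and two figures, and slightly more output to explain. No new data are needed.

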11.11.5.6. Safety Figures (Part C)

Safety: Figures					
No.	Population	IDSL / Example Shell	Title	Programming Notes	Deliverable [Priority]
Adverse Events					
3.1.	ITT (Part C)	AE10	Plot of Common ( $\geq 3\%$ ) On-treatment Adverse Events and Relative Risk (Part C)	IDSL $\geq 3\%$ (prior to rounding to nearest percent)	SAC
3.2.	ITT (Part C)	SHELL	Figure of On-treatment Serious Adverse Events and Adverse Events of Special Interest (Relative Risk, 100mg SC vs Placebo) (Part C)		SAC

**11.11.6. Part D****11.11.6.1. Study Population Tables (Part D)**

Study Population Tables					
No.	Population	IDSL / Example Shell	Title	Programming Notes	Deliverable [Priority]
Population Analysed					
1.35.	ASE	SHELL	Summary of Study Populations (Part D)	IDSL Include As Treated (Part D) Population	SAC
Subject Disposition					
1.36.	AT (Part D)	ES8	Summary of Subject Status and Reason for Study Withdrawal (Part D)	ICH E3, FDAAA, EudraCT	SAC
1.37.	AT (Part D)	SD1	Summary of Treatment Status and Reasons for Discontinuation of Study Treatment (Part D)	ICH E3	SAC
1.38.	ITT (Part D)	SHELL	Summary of Attendance at Each Clinic Visit (Part D)		SAC
Protocol Deviation					
1.39.	AT (Part D)	DV1	Summary of Important Protocol Deviations (Part D)	ICH E3	SAC
Exposure					
1.40.	AT (Part D)	SHELL	Summary of Exposure to Study Treatment (Part D)	ICH E3 See Study Population Table 1.1 (204471 'FINAL_01' reporting effort)	SAC

**11.11.6.2. Efficacy Tables (Part D)**

Efficacy: Tables					
No.	Population	IDSL / Example Shell	Title	Programming Notes	Deliverable [Priority]
Blood Eosinophils					
2.50.	AT (Part D)	SHELL	Summary of Blood Eosinophils (10  /L) (Part D)		SAC

**11.11.6.3. Efficacy Figures (Part D)**

Efficacy: Figures					
No.	Population	IDSL / Example Shell	Title	Programming Notes	Deliverable [Priority]
Blood Eosinophils					
2.18.	AT (Part D)	SHELL	Figure of Ratio to Baseline in Blood Eosinophils (Part D)		SAC

11.11.6.4. Safety Tables (Part D)

Safety: Tables					
No.	Population	IDSL / Example Shell	Title	Programming Notes	Deliverable [Priority]
Adverse Events (AEs)					
3.108.	AT (Part D)	SHELL	Overview of Adverse Events (Part D)		SAC
3.109.	AT (Part D)	AE1	Summary of On-Treatment Adverse Events by System Organ Class and Preferred Term (Part D)	ICH E3	SAC
3.110.	AT (Part D)	AE5	Summary of On-Treatment Adverse Events by Maximum Intensity by System Organ Class and Preferred Term (Part D)	ICH E3 Add a Total column across all severities	SAC
3.111.	AT (Part D)	AE3	Summary of Common ( $\geq 3\%$ ) On-treatment Adverse Events by Overall Frequency (Part D)	ICH E3 $\geq 3\%$ (prior to rounding to nearest percent)	SAC
3.112.	AT (Part D)	AE1	Summary of On-Treatment Drug-Related Adverse Events by System Organ Class and Preferred Term (Part D)	ICH E3	SAC
3.113.	AT (Part D)	AE5	Summary of On-Treatment Drug-Related Adverse Events by System Organ Class and Preferred Term and Maximum Intensity (Part D)	Add a Total column across all severities	SAC
3.114.	AT (Part D)	SHELL	Summary of On-Treatment Adverse Events by Age Group (12-17, 18-64, $\geq 65$ years) (Part D)		SAC
3.115.	AT (Part D)	SHELL	Summary of On-Treatment Adverse Events by Highest Anti Drug Antibody Result At Any Time On-Treatment (Part D)		SAC
3.116.	AT (Part D)	AE15	Summary of Common ( $\geq 3\%$ ) Non-serious On-Treatment Adverse Events by System Organ Class and Preferred Term (Number of Subjects and Occurrences) (Part D)	FDAAA, EudraCT $\geq 3\%$ (prior to rounding to nearest percent)	SAC
3.117.	AT (Part D)	AE1	Summary of On-Treatment Drug-Related Non-Serious Adverse Events by System Organ Class and Preferred Term (Part D)	Table required for plain language summary	SAC
Serious and Other Significant Adverse Events					
3.118.	AT (Part D)	AE1	Summary of On-Treatment Serious Adverse Events by System Organ Class and Preferred Term (Part D)		SAC

Safety: Tables					
No.	Population	IDSL / Example Shell	Title	Programming Notes	Deliverable [Priority]
3.119.	AT (Part D)	SHELL	Summary of On-Treatment Serious Adverse Events by Age Group (12-17, 18-64, ≥65 years) (Part D)		SAC
3.120.	AT (Part D)	AE1	Summary of On-Treatment Fatal Serious Adverse Events (Part D)		SAC
3.121.	AT (Part D)	SHELL	Summary of On-Treatment Fatal Serious Adverse Events by Age Group (12-17, 18-64, ≥65 years) (Part D)		SAC
3.122.	AT (Part D)	AE1	Summary of On-Treatment Non-Fatal Serious Adverse Events by System Organ Class and Preferred Term (Part D)		SAC
3.123.	AT (Part D)	AE1	Summary of On-Treatment Drug-Related Serious Adverse Events by System Organ Class and Preferred Term (Part D)	Table required for plain language summary	SAC
3.124.	AT (Part D)	AE1	Summary of On-Treatment Adverse Events Leading to Permanent Discontinuation of Study Treatment or Withdrawal from Study by System Organ Class and Preferred Term (Part D)	IDSL	SAC
3.125.	AT (Part D)	AE16	Summary of On-Treatment Serious Adverse Events by System Organ Class and Preferred Term (Number of Subjects and Occurrences) (Part D)	FDAAA, EudraCT	SAC
Adverse Events of Special Interest					
3.126.	AT (Part D)	SHELL	Summary of On-treatment Serious Adverse Events and Adverse Events of Special Interest (Part D)		SAC
3.127.	AT (Part D)	AE1	Summary of On-Treatment Systemic Reactions Meeting Anaphylaxis Criteria (Part D)	Present by Anaphylactic Criterion 1, 2 and 3 rather than SOC as shown in AE1 Insert footnote: "Events displayed are a subset of reactions defined by the Investigator as being systemic"	SAC
3.128.	AT (Part D)	SHELL	Summary Profile of On-Treatment Systemic Reactions Meeting Anaphylaxis Criteria (Part D)	Insert footnote: "Events displayed are a subset of reactions defined by the Investigator as being systemic"	SAC

Safety: Tables					
No.	Population	IDSL / Example Shell	Title	Programming Notes	Deliverable [Priority]
3.129.	AT (Part D)	AE1	Summary of On-Treatment Adverse Events Defined by the Investigator as Being Systemic (non-allergic or allergic/hypersensitivity) Reactions (Part D)		SAC
3.130.	AT (Part D)	SHELL	Summary Profile of On-Treatment Systemic (non-allergic or allergic/hypersensitivity) Reactions (Part D)		SAC
3.131.	AT (Part D)	SHELL	Summary Profile of On-Treatment Systemic Allergic Reactions (Part D)		SAC
3.132.	AT (Part D)	SHELL	Summary Profile of On-Treatment Systemic Non-Allergic Reactions (Part D)		SAC
3.133.	AT (Part D)	AE1	Summary of On-Treatment Adverse Events Defined by the Investigator as being Local Injection Site Reactions (Part D)		SAC
3.134.	AT (Part D)	SHELL	Summary Profile of On-Treatment Local Injection Site Reactions (Part D)		SAC
3.135.	AT (Part D)	AE1	Summary of On-Treatment Opportunistic Infections (Part D)		SAC
3.136.	AT (Part D)	SHELL	Summary Profile of On-Treatment Opportunistic Infections (Part D)		SAC
3.137.	AT (Part D)	AE1	Summary of On-Treatment Malignancies (Part D)		SAC
3.138.	AT (Part D)	SHELL	Summary Profile of On-Treatment Malignancies (Part D)		SAC
3.139.	AT (Part D)	AE1	Summary of On-Treatment Serious Cardiac, Vascular and Thromboembolic Adverse Events (Part D)		SAC
3.140.	AT (Part D)	SHELL	Summary Profile of On-Treatment Serious Cardiac, Vascular and Thromboembolic Adverse Events (Part D)		SAC
3.141.	AT (Part D)	AE1	Summary of On-Treatment Serious Ischemic Adverse Events (Part D)		SAC
3.142.	AT (Part D)	SHELL	Summary Profile of On-Treatment Serious Ischemic Adverse Events (Part D)		SAC
Cardiovascular Events and Deaths (All Causes)					
3.143.	AT (Part D)	SHELL	Summary of Cardiovascular Events and Deaths (All Causes) Reported by the Investigator (On-Treatment, Part D)		SAC

Safety: Tables					
No.	Population	IDSL / Example Shell	Title	Programming Notes	Deliverable [Priority]
Laboratory: Chemistry					
3.144.	AT (Part D)	LB1	Summary of Chemistry Changes from Baseline (On-Treatment, Part D)	ICH E3 Includes Baseline values.	SAC
3.145.	AT (Part D)	LB3	Summary of Chemistry Results (Changes from Baseline Relative to the Normal Range) (On-Treatment, Part D)	ICH E3	SAC
3.146.	AT (Part D)	LB3	Summary of Chemistry Results (Changes from Baseline Relative to the Reference Range [Potential Clinical Importance]) (On-Treatment, Part D)	ICH E3	SAC
Laboratory: Haematology					
3.147.	AT (Part D)	LB1	Summary of Haematology Changes from Baseline (On-Treatment, Part D)	ICH E3 Includes baseline values.	SAC
3.148.	AT (Part D)	LB3	Summary of Haematology Results (Changes from Baseline Relative to the Normal Range) (On-Treatment, Part D)	ICH E3	SAC
3.149.	AT (Part D)	LB3	Summary of Haematology Results (Changes from Baseline Relative to the Reference Range [Potential Clinical Importance]) (On-Treatment, Part D)	ICH E3	SAC
Laboratory: Hepatobiliary (Liver)					
3.150.	AT (Part D)	LIVER10	Summary of Hepatobiliary Laboratory Abnormalities (On-Treatment, Part D)	IDSL	SAC
ECG					
3.151.	AT (Part D)	EG1	Summary of ECG Findings (On-Treatment, Part D)	IDSL	SAC
3.152.	AT (Part D)	EG2	Summary of Change from Baseline in ECG Values by Visit (On-Treatment, Part D)	IDSL Includes Baseline values.	SAC
3.153.	AT (Part D)	SHELL	Summary of Actual and Change From Baseline QTc(F) Values by Category (msec) (On-Treatment, Part D)		SAC
3.154.	AT (Part D)	SHELL	Summary of Actual and Change From Baseline QTc(B) Values by Category (msec) (On-Treatment, Part D)		SAC

Safety: Tables					
No.	Population	IDSL / Example Shell	Title	Programming Notes	Deliverable [Priority]
Vital Signs					
3.155.	AT (Part D)	VS1	Summary of Change from Baseline in Vital Signs (On-Treatment, Part D)	ICH E3 Includes Baseline values.	SAC
Immunogenicity					
3.156.	AT (Part D)	SHELL	Summary of ADA Assay Results (On-Treatment, Part D)		SAC
3.157.	AT (Part D)	SHELL	Summary of Treatment Emergent ADA Assay Results (On-Treatment, Part D)		SAC
3.158.	AT (Part D)	SHELL	Summary of NAb Assay Results (On-Treatment, Part D)		SAC

